Cover Page

Official Title: Use of an Off-the-Shelf Exergame as an In-Bed Gamified Rehabilitation Intervention for Severely Deconditioned Inpatients: A Feasibility Study

NCT Number: NCT06937463 **Document Date:** 2026.05.14.

Principal Investigator: [name], Associate Professor, Department of Rehabilitation Medicine, Asan Medical Center

Study Implementation Institution: Asan Medical Center

Study Protocol and Statistical Analysis Plan

1. Study Overview

- **Background:** Patients often face limited mobility due to Intensive Care Unit Acquired Weakness (ICU-AW) or secondary sarcopenia after acute medical illnesses or surgeries. Traditional rehabilitation is often limited to monotonous movements due to postural restrictions. Exer-gaming (e.g., Nintendo Ring Fit) can increase motivation and improve exercise adherence.
- **Objective:** To explore the feasibility, safety, and adherence of a virtual reality-based rehabilitation program using Nintendo Ring Fit™ for hospitalized patients with limited mobility.
- **Study Design:** Prospective clinical study (Pilot study).
- **Study Duration:** From IRB approval date to October 31, 2025.

2. Participants

- **Target Sample Size:** 28 participants (calculated considering dropout rates for a pilot study).
- **Inclusion Criteria:**
 - Adult patients aged 18 years or older admitted with acute medical/surgical diseases.
 - Patients with limited mobility with a Functional Ambulatory Category (FAC) score of 3 or less.
 - Organ transplant recipients with history of critical care
 - Note: FAC 3 indicates a state requiring one guardian for supervision without physical contact during ambulation.
- **Exclusion Criteria:**
 - Unable to cooperate due to severe cognitive or consciousness impairment.
 - Continuous biomechanical instability.
 - Severe range of motion (ROM) or strength limitations, or amputation, preventing

exercise execution.

- Fractures or skeletal instability requiring movement restrictions.
- Difficulty cooperating due to vision or hearing impairment.

3. Interventions (Methods)

- **Rehabilitation Tool:** Exer-gaming using Nintendo Ring Fit™.
- **Protocol:**
 - **Duration & Frequency:** A total of 10 exercise sessions over 2 weeks (can be extended up to 1 month depending on the patient's condition).
 - **Session Time:** Within 30 minutes per session.
 - **Movements:** The program utilizes movements possible while lying down or sitting (e.g., upper limb, trunk, and lower limb exercises) customized to individual capabilities.

4. Outcome Measures

Assessments are conducted at baseline (Visit 1), interim (Visit 7), and completion (Visit 13), with continuous data collected during intervention sessions.

- **Clinical Assessments:**
 - Manual Muscle Test (MMT), Medical Research Council Sum Score (MRC-SS), Knee Extensor test, Grip strength test.
 - Modified Barthel Index, Mini-Mental State Examination (MMSE), Numeric Rating Scale (NRS) for pain.
 - Mobility/Balance: ASAN Mobility Score, ICU Mobility Scale, FAC, Sit to Stand test, Single Leg Raise (SLR) capability, Bridge capability, 10-Meter Walk Test (10MWT).
- **Engineering Indices (Multi-sensor Data):**
 - Physical measurements (activity level, ROM, speed, distance) utilizing camera-based motion recognition sensors and Inertial Measurement Units (IMU).
 - Built-in Nintendo Ring Fit™ score.

- **Patient-Reported Outcomes (PROs):**
 - Quality of life (EQ-5D), mood, subjective health/functional status.
 - Program satisfaction, acceptance, difficulty, and understanding.
- **Safety & Adherence:**
 - Session participation/discontinuation rates, reasons for dropout.
 - Heart rate monitoring via Polar monitor.
 - Occurrence of adverse events (falls, extubation, altered consciousness).
- **Exercise metrics:**
 - Net exercise time
 - exercise prescription, completion and fail records
 - exercise performance score(calculated by nintendo software) and repetition numbers

5. Statistical Analysis Plan

- **Software:** SPSS and R programs.
- **Significance Level:** $p < 0.05$.
- **Descriptive Statistics:** Baseline participants' demographic and clinical characteristics, compliance, exercise metrics, patient satisfaction, safety measures.
- **Normality Test:** Shapiro-Wilk test.
- **Categorical Variables:** Analyzed using Chi-square test, Fisher's exact test and Logistic regression.
- **Continuous Variables:** Analyzed using Mann-Whitney U test, Kruskal-Wallis test, Wilcoxon signed-rank test and Friedman test. Post hoc pairwise comparisons will be conducted using the Wilcoxon signed-rank test with Bonferroni correction.

Informed Consent Form Information

1. Study Title and Investigators

- **Title:** Feasibility of Exergame-Based Rehabilitation in Patients With Limited Mobility
- **Principal Investigator:** [name] (Dept. of Rehabilitation Medicine).

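### Adverse events are given as three named events and summarised without an interval, so a zero count would appear to say more about safety than it can

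*Combined protocol and SAP*

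**What the plan says.** The objective in section 1 is "To explore the feasibility, safety, and adherence of a virtual reality-based rehabilitation program" using a commercial exergame, in a study described as a prospective pilot. Section 2 sets the size at "28 participants (calculated considering dropout rates for a pilot study"; it states no dropout rate, evaluable number or precision target.

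Under Safety & Adherence, section 4 lists three items:

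- "Session participation/discontinuation rates, reasons for dropout"
- "Heart rate monitoring via Polar monitor"
- "Occurrence of adverse events (falls, extubation, altered consciousness"

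Pain is measured with a "Numeric Rating Scale (NRS) for pain", but under Clinical Assessments, which are scheduled for Visits 1, 7 and 13.

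In section 5, safety appears only in the list of things to be described: "compliance, exercise metrics, patient satisfaction, safety measures". No confidence interval, denominator or acceptable event rate is given.

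**The concern.** There are two gaps, and they compound each other.

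The first is definition. The parenthesis after adverse events contains three events and no 'e.g.', although the document uses 'e.g.' where it means examples (the Background in section 1, the Movements item in section 3). An analyst following the text would count those three and nothing else. A musculoskeletal injury, a wound or line problem, or a painful session would have no place in the adverse event count. Without a window, it is also unclear whether a listed event counts if it happens between sessions or during a scheduled assessment such as the walk test.

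The second is uncertainty. A descriptive summary of a rare outcome in a small group is often a zero. Without an interval, a zero carries no indication of how large a risk is still compatible with the data.

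Together they allow a report of no adverse events that is literally in line with the plan, yet silent both on events outside the list and on how little 28 patients can exclude. As safety is a stated objective, this affects what the study may conclude.

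**Working it through.** **Inputs from the documents.** N = 28 (section 2); 10 sessions per patient (section 3); safety described only, with no interval (section 5). The documents state neither a confidence level nor sidedness for intervals, so both 95% conventions are shown.

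**The plan's own figure.** N = 28 cannot be reproduced, because neither a base number nor a dropout rate is given. Several assumed pairs lead to it: 25/(1 − 0.10) = 27.8, 23/(1 − 0.15) = 27.1 and 22/(1 − 0.20) = 27.5 all round up to 28. The number is therefore not identified, but it is not shown to be wrong.

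**Upper limit with zero events.** For 0 events in n patients, the exact (Clopper-Pearson) two-sided 95% upper limit is 1 − 0.025^(1/n), and the one-sided 95% limit is 1 − 0.05^(1/n). For n = 28:

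- two-sided: 1 − 0.025^(1/28) = 12.3%
- one-sided: 1 − 0.05^(1/28) = 10.1%
- cross-checks: Wilson two-sided upper limit 12.1%; rule of three 3/28 = 10.7%, against the one-sided limit

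**Sensitivity to the evaluable number** (n below 28 is assumed):

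| n | two-sided 95% upper limit | one-sided 95% upper limit |
|---|---|---|
| 28 | 12.3% | 10.1% |
| 25 | 13.7% | 11.3% |
| 22 | 15.4% | 12.7% |
| 20 | 16.8% | 13.9% |

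**Chance of seeing nothing.** If the true per-patient risk is p, the probability of no event in 28 is (1 − p)^28. For p = 5% it is 0.95^28 = 24%; for p = 10% it is 0.90^28 = 5%.

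**One event instead of none.** For 1/28, the exact two-sided 95% interval is 0.1% to 18.3%.

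**Why not use sessions.** 28 × 10 = 280 planned sessions, and 0/280 would give 1 − 0.025^(1/280) = 1.3%. That treats sessions within a patient as independent, so it should not replace the per-patient limit.

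These figures quantify only the missing interval. They follow from n alone and would be the same under a complete adverse event definition. The definition gap rests on the wording and cannot be sized from the documents.

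**The case against.** The strongest reply has four parts.

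*Safety does not rest on three events alone.* This stands. Discontinuation rates, reasons for dropout and heart rate sit under the same heading and fall within the safety measures to be described. A harm that ended participation could surface there. But no rule says when any of these becomes an adverse event, and the reason for stopping a single session short of dropout is not clearly captured.

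*The list is not expressly closed.* This also stands. A reader might infer that the plan excludes other harms; it does not say so, and a fuller recording procedure may exist outside this short document. Omission is a risk of the wording, not a stated rule. That is a reason to settle the wording.

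*The study is exploratory.* Correct. The plan sets no safety threshold and claims to exclude no risk, so 28 is not an error. The interval is needed to report the result honestly, whatever the size of the study.

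*Zero is not built in.* A reader might infer that the listed events could hardly occur in a lying or seated programme. The documents do not support that. They give no event rates and do not say how many patients are intubated. Patients have FAC 3 or less, and the assessments include a sit-to-stand test and a 10-metre walk.

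**Conclusion.** The point holds as a gap in definition and reporting. Read literally, the adverse event outcome is a count of three named events, described without an interval. The related items under the safety heading are not defined as adverse events.

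The size of the reporting gap is an upper limit of 12.3% for 0/28 (two-sided 95%, exact) or 10.1% (one-sided 95%). Both assume zero events and all 28 patients in the denominator; fewer patients widen them.

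A reader might go further and say that the study cannot exclude a 12% risk. That depends on the convention. At a true risk of 12%, the chance of no event is 0.88^28 = 2.8%, which lies between 2.5% and 5%. The two-sided limit therefore leaves 12% in (29 event-free patients would be needed to exclude it), while the one-sided limit rules it out (24 suffice). The documents choose neither.

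This is a cheap improvement, not a flaw in the design.

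**What to change.** - Define the safety outcome as any untoward event recorded during the intervention period, with falls, extubation and altered consciousness as a named subset.
- Report patients with at least one event among all who started at least one session, with an exact (Clopper-Pearson) 95% interval. Carry the upper limit into the safety conclusion.
- Tabulate discontinuations for medical reasons and the heart-rate data descriptively alongside.

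**If collection is finished.** The stated study period ends on October 31, 2025 and the document is dated 2026.05.14, so recording may no longer be changeable. In that case, state what was recorded. If it was only the three events, write *none of the three prespecified events* with the interval, not *no adverse events*. Label any added definition post hoc.

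**Not recommended.** Three further additions may suggest themselves, but the documents do not support them:

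- A count of heart-rate excursions for each patient: no individual range is stated.
- A session-level pain summary: the NRS is scheduled only at Visits 1, 7 and 13.
- A cluster-robust per-session interval: with no events its estimated variance is zero, so it fails in the case that matters.

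**Cost.** A few sentences of definition and one table; if recording is still open, a general adverse event entry as well. More minor events will be reported and the safety statement will be more cautious. Patient management does not change.

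### The SAP names no paired method for categorical outcomes, although SLR and Bridge capability are assessed at three visits in the same patients

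*Combined protocol and SAP*

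**What the plan says.** Section 1 (Study Overview) describes a single prospective pilot study. No control arm, randomisation or subgroup is defined. Section 2 (Participants) sets the target at 28, and Section 3 (Interventions) plans "A total of 10 exercise sessions over 2 weeks".

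Section 4 (Outcome Measures) fixes the timing: "Assessments are conducted at baseline (Visit 1), interim (Visit 7), and completion (Visit 13), with continuous data collected during intervention sessions". The mobility and balance items include "FAC, Sit to Stand test, Single Leg Raise (SLR) capability, Bridge capability". Under exercise metrics it also collects "exercise prescription, completion and fail records".

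Section 5 (Statistical Analysis Plan) deals with categorical variables in one line: "Analyzed using Chi-square test, Fisher's exact test and Logistic regression". It names no McNemar test, Cochran's Q, conditional logistic model, GEE or mixed model. The line for continuous variables lists both independent-group tests (Mann-Whitney, Kruskal-Wallis) and within-patient tests (Wilcoxon signed-rank, Friedman), with Bonferroni-corrected pairwise comparisons. A separate line assigns baseline characteristics, compliance, exercise metrics, satisfaction and safety to description. The plan does not say which categorical variable goes to which test, or whether a comparison is between or within patients.

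**The concern.** The continuous line shows that change within patients is to be analysed. For a yes/no outcome measured at three visits, an analyst who follows the plan literally has only unpaired methods available. A chi-square or Fisher test on a visit-by-capability table, or an ordinary logistic regression with visit as covariate, treats 28 × 3 = 84 records as 84 different people.

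When a patient's records are positively correlated, change between visits varies less than those methods assume. Their p-values are then too large and real improvement is missed. With 28 patients at most, there is little power to spare.

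**Working it through.** **Inputs from the documents.** 28 patients; 3 assessment visits; 10 sessions; significance level 0.05. The documents give no effect size, power or dropout percentage, so the figure of 28 cannot be reproduced, and this point does not dispute it.

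**Assumptions, not in the documents.** SLR and Bridge are scored yes/no. Latent within-patient correlation is 0.3 to 0.8. The illustrative proportions able are 0.30, 0.45 and 0.60 at Visits 1, 7 and 13. Session-level ICC is 0.05 to 0.5. All 28 patients are observed at all three visits.

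**1. Type I error across visits.** With a common proportion p and a correlation φ between any two visits, the variance of the difference between two visits is 2p(1 − p)(1 − φ)/28. The unpaired test uses 2p(1 − p)/28. The three-visit chi-square statistic is therefore shrunk by about (1 − φ), and its true size is about 0.05^(1/(1 − φ)). Simulation at p = 0.5:

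| Latent correlation | φ | Formula | Simulated chi-square | Simulated Cochran's Q |
|---|---|---|---|---|
| 0.3 | 0.19 | 2.5% | 2.7% | 5.0% |
| 0.6 | 0.41 | 0.6% | 0.7% | 5.0% |
| 0.8 | 0.59 | 0.07% | 0.12% | 5.0% |

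Over p = 0.30, 0.45 and 0.50 the simulated chi-square size runs from about 0.1% to 2.8%. Cochran's Q stays within 4.9% to 5.1%.

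**2. Power across visits, for 0.30 to 0.45 to 0.60.**

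| Latent correlation | Chi-square | Cochran's Q |
|---|---|---|
| 0 | 53% | 51% |
| 0.3 | 51% | 60% |
| 0.6 | 49% | 74% |
| 0.8 | 46% | 87% |

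With no correlation the two tests are about equal. The gain from pairing grows with the correlation.

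**3. A single table does not settle it.** Take 10/28 able at Visit 1 and 18/28 at Visit 13. Uncorrected chi-square is 4.57, p = 0.033; with continuity correction p = 0.061; Fisher p = 0.060. Exact McNemar depends on how many gained and how many lost the ability:

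| Gained vs lost | Exact McNemar p |
|---|---|
| 8 vs 0 | 0.008 |
| 9 vs 1 | 0.021 |
| 10 vs 2 | 0.039 |
| 11 vs 3 | 0.057 |
| 12 vs 4 | 0.077 |

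The last row is close to no association: 10 − 4 = 6 patients able at both visits, against 10 × 18/28 = 6.4 expected under independence. So the paired test does not give the smaller p-value in every table, and the argument rests on steps 1 and 2.

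**4. Session records, only if they are analysed inferentially.** Up to 28 × 10 = 280 records. Design effect = 1 + (10 − 1) × ICC. At ICC 0.05, 0.2 and 0.5 it is 1.45, 2.8 and 5.5. The 280 records are then worth 280/1.45 = 193, 280/2.8 = 100 and 280/5.5 = 51. Standard errors that treat the records as independent are too small by factors of √1.45 = 1.20, √2.8 = 1.67 and √5.5 = 2.35. Here the error is anti-conservative, the opposite of step 1.

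**The case against.** The strongest reply is that the plan never commits to using these tests on repeated records. Mann-Whitney and Kruskal-Wallis suggest that some between-patient comparisons are intended, and chi-square, Fisher and logistic regression are their categorical counterparts. Dropout, any adverse event and baseline categories can each be one record per patient, and for those the listed tests are appropriate: in a simulation of 14 versus 14 patients, Fisher's type I error was 2.3%, below the nominal 5%. This stands. A reader might infer that every categorical p-value in the trial would be wrong; the documents do not support that.

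A reader might also infer that completion and fail records will be pooled and tested as 280 independent observations. The plan lists compliance and exercise metrics under description and plans no test or interval on pooled sessions. That part is a warning, not an error in the plan.

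Two further points stand. Yes/no scoring of SLR and Bridge is inferred from the word capability; if they are graded, the listed Friedman and Wilcoxon tests could serve. And at visit level the error is conservative, so it would not produce false claims of benefit, in a pilot whose objective is feasibility, safety and adherence.

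What the reply leaves untouched is the gap itself. SLR and Bridge are outcomes at three visits, follow-up values of these are not in the descriptive list, and no method in the categorical line respects the pairing.

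**Conclusion.** The plan lacks a within-patient method for binary outcomes. If the listed tests are applied to SLR or Bridge capability across Visits 1, 7 and 13, they are too conservative: type I error of about 0.1% to 2.8% against 5%, and, for the assumed rise, 9 to 41 percentage points less power than Cochran's Q (60% − 51% to 87% − 46%). These figures rest on yes/no scoring, complete data on 28 patients, and assumed correlations and proportions; the direction needs only positive correlation within patients. The listed tests remain sound for between-patient comparisons with one record per patient. The session-level problem arises only if those records are tested, modelled or given an interval. Severity is moderate: the affected items are two among many clinical assessments in a feasibility pilot, but the omission is plain and cheap to repair.

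**What to change.** Replace the categorical line with a short paragraph that states the unit of analysis for each variable:

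- **Binary outcomes compared across Visits 1, 7 and 13** (SLR and Bridge capability, if yes/no): Cochran's Q, then exact McNemar pairwise tests with Bonferroni correction, reporting the paired difference in proportions with a 95% CI. State how SLR and Bridge are scored and how patients with a missed visit are handled.
- **Ordinal scales such as FAC:** the Friedman and Wilcoxon signed-rank tests already listed.
- **One record per patient** (for example dropout or any adverse event), compared between patients: keep chi-square, Fisher's exact and logistic regression, and name the groups.
- **Session-level completion and fail records:** descriptive, as planned. If they are tested, modelled or given an interval, use per-patient proportions or a model clustered on participant (logistic GEE with small-sample correction, or mixed logistic regression).

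The cost is one SAP paragraph and a few lines of R. No new data are needed.

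### The Friedman and paired Wilcoxon tests estimate functional change mainly in patients who finish, and no missing-data rule is given; add an all-observed-data model and replace Bonferroni with Holm

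*Combined protocol and SAP*

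**What the plan says.** Section 4 sets three assessment times: "Assessments are conducted at baseline (Visit 1), interim (Visit 7), and completion (Visit 13), with continuous data collected during intervention sessions". For continuous variables, section 5 lists rank methods only: "Analyzed using Mann-Whitney U test, Kruskal-Wallis test, Wilcoxon signed-rank test and Friedman test". It then adds: "Post hoc pairwise comparisons will be conducted using the Wilcoxon signed-rank test with Bonferroni correction".

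Dropout is anticipated. The target of 28 in section 2 was "calculated considering dropout rates for a pilot study", and section 4 makes "Session participation/discontinuation rates, reasons for dropout" an outcome. In section 3 the ten-session programme is planned over two weeks but "can be extended up to 1 month depending on the patient's condition".

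Section 5 names no analysis set, missing-data rule or sensitivity analysis. It does not say whether pairs are tested only after a significant Friedman result, or how many comparisons the Bonferroni correction covers.

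**The concern.** A severely deconditioned inpatient who leaves before Visit 13 contributes nothing to the Friedman test, even with Visits 1 and 7 recorded. The three pairwise tests may each rest on a different set of patients. The reported change could then describe those who stayed and be read as change in everyone enrolled. If leaving is related to recovery or deterioration, that estimate is biased, and a reader cannot tell which way. At a planned 28, discarding observed visits also costs precision, and Bonferroni over the visit pairs costs some more.

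**Working it through.** **1. The plan's own figure.** The target of 28 cannot be reproduced, because no effect size, SD, power or dropout rate is given. With assumed dropout d, the expected number of complete cases is 28 × (1 − d): 25.2, 22.4, 19.6 and 16.8 at d = 10%, 20%, 30% and 40%.

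**2. Which data each method uses.**

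| Visits observed | Friedman | Wilcoxon 1–7 | Wilcoxon 1–13 | Wilcoxon 7–13 | Repeated-measures model |
|---|---|---|---|---|---|
| 1, 7, 13 | yes | yes | yes | yes | yes |
| 1, 7 | no | yes | no | no | yes |
| 1, 13 | no | no | yes | no | yes |
| 1 only | no | no | no | no | yes |

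**3. Direction and size of bias (all inputs assumed).** Let r be the correlation between a patient's change and staying, under a normal model. The shift in mean change among stayers, in SDs of change, is r × φ(z_d) / (1 − d), where z_d is the d-quantile of the standard normal. For d = 20% and r = 0.5: 0.5 × 0.280 / 0.80 = 0.175. Simulation agrees:

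| Dropout | Better responders stay (r = +0.5) | Unrelated (r = 0) | Better responders leave (r = −0.5) |
|---|---|---|---|
| 10% | +0.10 | 0.00 | −0.10 |
| 20% | +0.18 | 0.00 | −0.17 |
| 30% | +0.25 | 0.00 | −0.26 |
| 40% | +0.32 | 0.00 | −0.32 |

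In baseline-SD units, assume true changes of 0.25 (Visit 7) and 0.50 (Visit 13), between-visit correlation 0.7 and 24% dropout decided by the Visit 1–7 change.

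- SD of change = √(2 × (1 − 0.7)) = 0.775.
- Correlation between the two changes = (1 − 0.7) / (2 × (1 − 0.7)) = 0.5.
- With a sharp cut-off, the shift = 0.5 × (0.311 / 0.76) × 0.775 = 0.16.
- Finishers show 0.50 + 0.16 = 0.66 if poor responders leave, and 0.50 − 0.16 = 0.34 if good responders leave.

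Less strict selection at the same dropout rate gave 0.58 to 0.64 and 0.37 to 0.42.

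**4. What a likelihood model recovers.** When dropout depends only on the observed Visit 7 response (missing at random), an unstructured likelihood analysis gave 0.50 (simulated mean 0.497). When dropout depends on the unseen Visit 13 change, it gave 0.76 at 24% dropout. In a separate run at about 27% it gave 0.73, against 0.79 in completers. The true value was 0.50 throughout, so in that case the model removes little of the bias.

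**5. Power.** With the step 3 effects and Friedman-gated Bonferroni pairs, power for Visit 1–13 is 67% with 28 complete cases and 52% with 21 (25% loss). This compares no dropout with complete cases; it does not show how much of the loss a model would recover.

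**6. Multiplicity.** Three visits give three pairs. If those are the family, the Bonferroni level is 0.05 / 3 = 0.0167. Simulated family-wise error with no true change, n = 28:

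| Procedure | Not gated on Friedman | Gated on Friedman |
|---|---|---|
| Unadjusted pairs | 12.2% | 4.2% |
| Bonferroni | 4.3% | 2.5% |

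Gated unadjusted pairs also stay at 4.3% to 4.7% when only one pair is null, but this assumes a common patient set. Holm compares the ordered p-values with 0.05/3, 0.05/2 and 0.05. Its first step is the Bonferroni step, so its error with no true change equals Bonferroni's, and it can never reject less. With the step 3 effects at n = 28 and no gate, Visit 1–7 power is 21% with Bonferroni and 27% with Holm. With a gate, it is 20% with Bonferroni and 32% unadjusted.

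**The case against.** The objective is feasibility, safety and adherence; functional change is secondary. Early leavers do not disappear from the report, because discontinuation and its reasons are outcomes and compliance is described. A Visit 1–7 Wilcoxon test keeps a patient who lacks only Visit 13. Many of the scales are ordinal or bounded, so rank tests are reasonable at n = 28. Bonferroni is conventional and controls error. A mixed model brings assumptions of its own.

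All of this stands, and it limits the point. It does not supply a missing-data rule, and section 5 still commits to tests at p < 0.05 on functional scales.

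Three stronger readings are tempting, and the documents do not support them:

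- A reader might infer that change will be overstated. No dropout rate or mechanism is given, and recovery with early discharge would understate it.
- A reader might infer that the Bonferroni step is pointless. That is so only if pairs are gated on Friedman and tested in one common set of patients. The term post hoc suggests a gate, but section 5 does not state one; without it, unadjusted pairs reach about 12% error.
- A reader might infer that a likelihood model removes the bias. It does so only under missing-at-random (step 4).

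**Conclusion.** The point holds as a moderate one. The Friedman test excludes anyone without all three visits, contrasts with Visit 13 exclude anyone without Visit 13, and the plan has no rule for missing visits. Estimated change may be biased in either direction. In the scenario worked through, the error is about 0.16 SD either way on a true 0.50, and it is zero if leaving is unrelated to change. Bonferroni is valid but conservative; using Holm instead is a small gain (21% to 27% for the smaller contrast), not the correction of an error. Neither method adjusts across the many outcomes.

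The exclusion of incomplete patients follows from the tests themselves. The sizes rest on assumed dropout rates, effects, correlations and normal data, since the documents give none of these. The feasibility objective is not threatened.

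**What to change.** - **Main analysis, continuous scales:** a repeated-measures model with visit as a factor, on all enrolled patients with at least one assessment. Report Visit 1–7 and Visit 1–13 change with 95% confidence intervals and n per visit.
- **No days-since-baseline term in the main model.** Days are zero for everyone at baseline, so with visit as a factor the term turns the visit contrast into change net of elapsed time. Because extension depends on the patient's condition, it would also adjust for a consequence of clinical course.
- **Ordinal scales:** a cumulative-logit mixed model, or keep the rank tests.
- **Checks:** keep Friedman and Wilcoxon as a completer analysis, and add a simple sensitivity analysis for informative dropout, such as shifting the assumed values of those who left up and down.
- **Multiplicity:** state the family and use Holm, which holds with or without a Friedman gate. Use unadjusted pairs only if the plan states the gate and a common patient set.

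The cost is SAP wording and modest programming, with no new data. The model relies on approximate normality and missing-at-random at n = 28, which is why the rank tests and the sensitivity analysis stay. The document is dated after the stated end of the study, so if results have already been seen, label the model as a later addition.
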